### 1.3.2. Benefit assessment

Benefit considerations include:

- Medical evaluations/assessments associated with this study (e.g. physical examinations).
- Contributing to the process of developing new therapies in an area of unmet need.
- Potential benefit of receiving the licensed rMenB+OMV NZ and MenACWY vaccines.

### 1.3.3. Overall benefit : risk conclusion

No significant safety signals have been identified for MenABCWY. Cumulative safety data have not identified new important safety risks. The balance of anticipated benefits and apparent risks associated with MenABCWY continues to be acceptable following the ongoing systematic review of safety data.

Taking into account the measures taken to minimize risk to subjects participating in this study, the potential or identified risks identified in association with rMenB+OMV NZ, MenACWY, and MenABCWY are justified by the potential benefits (prevention/treatment) that may be afforded to subjects.

## 2. OBJECTIVES

### 2.1. Primary objective

- To assess the immune response to 2 doses of MenABCWY, rMenB+OMV NZ, or rMenB+OMV NZ and MenACWY administered concomitantly in the same arm or in 2 different arms, and to a single dose of MenACWY at 1 month after the last vaccination.

Refer to Section 10.1 for the definition of the primary endpoint.

## 2.2. Secondary objectives

### Immunogenicity Objective

- To assess the immune response to 2 doses of MenABCWY, rMenB+OMV NZ, or rMenB+OMV NZ and MenACWY administered concomitantly in the same arm or in 2 different arms at 1 month after the first vaccination.

### Safety Objective

- To assess the safety and tolerability of 2 doses of MenABCWY, rMenB+OMV NZ, or rMenB+OMV NZ and MenACWY administered concomitantly in the same arm or in 2 different arms, and to a single dose of MenACWY.

Refer to Section [10.2](#) for the definition of the secondary endpoints.

## 2.3. Tertiary objective

- *To further characterize the immune response induced by the study vaccine(s) against an additional panel of strains of Neisseria species in a subset of subjects.*

[figure not shown]
*Note: This tertiary objective is exploratory and suitable assays may or may not be developed. The tertiary objective will be assessed in a subset of subjects using remaining serum after the primary and secondary analyses have been completed; no additional blood samples will be collected from subjects. Any outcome of exploratory testing that would be of scientific/medical relevance will be reported in an annex/addendum to the final study report.*

Refer to Section [10.3](#) for the definition of the tertiary endpoint and to Section [10.11.1](#) for the reporting of tertiary endpoint results.

(Amended 29 Aug 2018)

## 3. STUDY DESIGN OVERVIEW

The study design diagram is provided in [Figure 1](#).

**Figure 1** Study design diagram

A list of procedures that may be performed before Visit 1 is detailed in [Table 4](#).

Protocol waivers or exemptions are not allowed unless necessary for the management of immediate safety concerns. Therefore, adherence to the study design requirements, including those specified in the outline of study procedures (Section [5.5](#)), are essential and required for study conduct.

- Experimental design: Phase II, open-label, randomized, controlled, multi-centric, study with 5 parallel study groups
- Duration of the study: Up to 91 days (4 visits, 30 days apart)
  - Epoch 001: Starting at Visit 1 (Day 1) and ending at Visit 4 (Day 91)
- Primary Completion Date (PCD): Visit 4 (Day 91)
 

Refer to [glossary of terms](#) for the definition of PCD.
- End of Study (EoS): Date of the last testing results released for the samples collected at Visit 4 (Day 91), to be achieved no later than 8 months after the Last Subject Last Visit (LSLV)
 

Refer to [glossary of terms](#) for the definition of EoS.

- Study groups:

Approximately 500 subjects will be randomly assigned at a 1:1:1:1:1 ratio to receive one of the following:

- MenABCWY: Approximately 100 subjects (50 subjects aged 10 to 17 years and 50 subjects aged 18 to 25 years) will receive 1 intramuscular (IM) dose of MenABCWY twice, 2 months apart.
- rMenBOMV+ACWY\_S: Approximately 100 subjects (50 subjects aged 10 to 17 years and 50 subjects aged 18 to 25 years) will concomitantly receive 1 IM dose of rMenB+OMV NZ and 1 IM dose of MenACWY in the same arm (approximately 2.5 cm apart) twice, 2 months apart.
- rMenBOMV+ACWY\_D: Approximately 100 subjects (50 subjects aged 10 to 17 years and 50 subjects aged 18 to 25 years) will concomitantly receive 1 IM dose of rMenB+OMV NZ and 1 IM dose of MenACWY in 2 different arms twice, 2 months apart.
- rMenBOMV: Approximately 100 subjects (50 subjects aged 10 to 17 years and 50 subjects aged 18 to 25 years) will receive 1 IM dose of rMenB+OMV NZ twice, 2 months apart.
- MenACWY: Approximately 100 subjects (50 subjects aged 10 to 17 years and 50 subjects aged 18 to 25 years) will receive 1 IM dose of MenACWY once.

**Table 1 Study groups and epochs foreseen in the study**

Study groups	Number of subjects 	Age (Min – Max)	Epochs	
			Epoch 001	
MenABCWY	100	10 years – 25 years		x
rMenBOMV+ACWY_S 	100	10 years – 25 years		x
rMenBOMV+ACWY_D 	100	10 years – 25 years		x
rMenBOMV	100	10 years – 25 years		x
MenACWY	100	10 years – 25 years		x

Approximate number of subjects.

S refers to administration in the same arm (approximately 2.5 cm apart).

D refers to administration in 2 different arms.

**Table 2 Study groups and treatment foreseen in the study**

Treatment name	Vaccine name	Study groups				
		MenABCWY	rMenBOMV +ACWY_S 	rMenBOMV +ACWY_D 	rMenBOMV	MenACWY
MenABCWY	MenACWY lyo	x				
	rMenB+OMV NZ					
rMenB+OMV NZ	rMenB+OMV NZ		x	x	x	
MenACWY	MenA lyo		x	x		x
	MenCWY liquid					

S refers to administration in the same arm (approximately 2.5 cm apart).

D refers to administration in 2 different arms.

- Control: active control
- Vaccination schedules: First vaccination at Visit 1 (Day 1) and second vaccination at Visit 3 (Day 61), with the exception of the MenACWY study group, which will have only 1 vaccination at Visit 1 (Day 1)
- Treatment allocation: Randomization will be performed prior to or at Visit 1 (Day 1). The randomization list will be generated using MATerial EXcellence (MATEX). Central randomization will be performed using the Source DataBase for Internet Randomization (SBIR) system.
- Blinding: Open-label

**Table 3 Blinding of study epochs**

Study Epochs	Blinding
Epoch 001	Open

- Sampling schedule: Blood samples of approximately 20 mL will be taken at Visit 1, Visit 2, and Visit 4, with the exception of the MenACWY study group, which will have blood samples collected only at Visit 1 and Visit 2
- Type of study: Self-contained
- Data collection: Standardized eCRF; solicited symptoms will be collected using a subject paper diary (pDiary)

## 4. STUDY COHORT

### 4.1. Number of subjects/centers

The target enrollment will be approximately 500 subjects (approximately 100 subjects per study group). Refer to Section 10.3 for a detailed description of the criteria used in the determination of sample size.

Overview of the recruitment plan:

- This is a multicenter study.
- Enrollment will be terminated when approximately 500 subjects have been enrolled.
- The recruitment and randomization will be monitored by SBIR.

### 4.2. Inclusion criteria for enrollment

Deviations from inclusion criteria are not allowed because they can potentially jeopardize the scientific integrity, regulatory acceptability of the study, or subject safety. Therefore, adherence to the criteria as specified in the protocol is essential.

All subjects must satisfy ALL the following criteria at study entry:

1. Subjects and/or subjects' parent(s)/Legally Acceptable Representative(s) (LARs) who, in the opinion of the investigator, can and will comply, with the requirements of the protocol (e.g. completion of the pDiary, return for follow-up visits, availability for all visits scheduled in the study).
2. Written informed consent obtained from the subject and/or from the parent(s)/LAR(s) of the subject prior to performing any study specific procedure.
3. Written informed assent obtained from subjects below the legal age of consent prior to performing any study specific procedure.
4. A male or female between, and including, 10 to 25 years of age at the time of the first vaccination.
5. Healthy subjects as established by medical history and clinical examination before entering into the study.
6. Female subjects of non-childbearing potential may be enrolled in the study.
  - Non-childbearing potential is defined as pre-menarche, current bilateral tubal ligation or occlusion, hysterectomy, or bilateral ovariectomy.

Please refer to the [glossary of terms](#) for the definition of menarche.

7. Female subjects of childbearing potential may be enrolled in the study, if the subject:
  - has practiced highly effective for 30 days prior to vaccination, and
  - has a negative pregnancy test on the day of vaccination, and
  - has agreed to continue highly effective contraception during the entire treatment period and for 2 months after completion of the vaccination series.

Please refer to the [glossary of terms](#) for the definition of highly effective contraception.

#### **4.3. Exclusion criteria for enrollment**

Deviations from exclusion criteria are not allowed because they can potentially jeopardize the scientific integrity, regulatory acceptability of the study, or subject safety. Therefore, adherence to the criteria as specified in the protocol is essential.

The following criteria should be checked at the time of study entry. If ANY exclusion criterion applies, the subject must not be included in the study:

1. Female planning to become pregnant or planning to discontinue contraceptive precautions.
2. Pregnant or lactating female.
3. Child in care.

Please refer to the [glossary of terms](#) for the definition of child in care.

Each subject must not have:

4. Current or previous, confirmed or suspected disease caused by *N. meningitidis*.

5. Known contact to an individual with any laboratory-confirmed *N. meningitidis* infection within 60 days prior to enrollment.
6. Previous vaccination against *N. meningitidis* at any time prior to informed consent.
7. Progressive, unstable or uncontrolled clinical conditions.
8. Hypersensitivity, including allergy, to any component of vaccines, medicinal products or medical equipment whose use is foreseen in this study.
9. Clinical conditions representing a contraindication to IM vaccination and blood draws.
10. Abnormal function of the immune system resulting from:
  - Clinical conditions.
  - Systemic administration of corticosteroids (oral/intravenous/IM) for more than 14 consecutive days within 90 days prior to informed consent.
  - Administration of antineoplastic and immune-modulating agents or radiotherapy within 90 days prior to informed consent.
11. Received immunoglobulins or any blood products within 180 days prior to informed consent.
12. Received an investigational or non-registered medicinal product within 30 days prior to informed consent.
13. Any other clinical condition that, in the opinion of the investigator, might interfere with the results of the study or pose additional risk to the subject due to participation in the study.
14. Concurrently participating in another clinical study, at any time during the study period, in which the subject has been or will be exposed to an investigational or a non-investigational vaccine/product (pharmaceutical product or device).
15. Acute or chronic, clinically significant pulmonary, cardiovascular, hepatic, or renal functional abnormality, as determined by physical examination.
16. Any confirmed or suspected immunosuppressive or immunodeficient condition, based on medical history and physical examination (no laboratory testing required).
17. Are obese at screening (e.g. with a body mass index [BMI]  $\geq 30 \text{ kg/m}^2$ , where BMI reflects obesity and not high muscle mass).
18. Family history of congenital or hereditary immunodeficiency.
19. History of neuroinflammatory or autoimmune condition.
20. History of significant neurological disorder or seizure (history of febrile convulsion should not lead to exclusion).
21. Serious chronic illness.
22. History of chronic alcohol consumption and/or drug abuse (including current consumption/abuse).
23. Any study personnel as an immediate family or household member.

24. Administration of a vaccine not foreseen by the study protocol in the period starting 14 days (for inactivated vaccines), 28 days (for live vaccines), or 7 days (for influenza vaccines) before each dose and ending 14 days (for inactivated vaccines), 28 days (for live vaccines), or 7 days (for influenza vaccines) after each dose of study vaccine(s) administration.

25. Thrombocytopenia, bleeding disorders, or be receiving anticoagulant therapy.

## **5. CONDUCT OF THE STUDY**

### **5.1. Regulatory and ethical considerations, including the informed consent process**

The study will be conducted in accordance with all applicable regulatory requirements.

The study will be conducted in accordance with the International Council for Harmonisation (ICH) Guideline for Good Clinical Practice (GCP), all applicable subject privacy requirements and the guiding principles of the Declaration of Helsinki.

The study has been designed and will be conducted in accordance with the ICH Harmonised Tripartite Guideline for clinical investigation of medicinal products in the pediatric population (ICH E11) and all other applicable ethical guidelines.

PPD, the contract research organization for this study, will obtain favorable opinion/approval to conduct the study from the appropriate regulatory agency, in accordance with applicable regulatory requirements, prior to a site initiating the study in that country.

Conduct of the study includes, but is not limited to, the following:

- Institutional Review Board/Independent Ethics Committee review and favorable opinion/approval of study protocol and any subsequent amendments.
- Subject/subject's parent(s)/LAR(s) informed consent and subject informed assent, as appropriate.
- Investigator reporting requirements as stated in the protocol.

PPD will provide full details of the above procedures to the investigator, either verbally, in writing, or both.

Freely given and written or witnessed/thumb printed informed consent must be obtained from each subject and/or each subject's parent(s)/LAR(s) and subject informed assent, as appropriate, prior to participation in the study.

PPD will prepare a model informed consent form (ICF) which will embody the ICH GCP and GSK Biologicals required elements. While it is strongly recommended that this model ICF is to be followed as closely as possible, the informed consent requirements given in this document are not intended to pre-empt any local regulations which require additional information to be disclosed for informed consent to be legally effective.

Clinical judgement, local regulations and requirements should guide the final structure and content of the local version of the ICF.

In accordance with the ICH Harmonised Tripartite Guidelines for GCP, those subjects who can only be enrolled in the study with the consent of the subject's parent(s)/LAR(s) (e.g. minors), should be informed about the study to the extent compatible with the subject's understanding and the subject should sign and personally date a written informed assent form (IAF). It is required that the assent be signed by each subject in addition to the informed consent that is to be signed by his/her parent(s)/LAR(s).

PPD strongly recommends that if the subject reaches the age of consent during the study they will be asked to provide consent at the next study visit (if applicable). This procedure should be applied according to local laws and regulations.

The investigator has the final responsibility for the final presentation of the ICF and IAF, respecting the mandatory requirements of local regulations. The ICF and IAF generated by the investigator with the assistance of the sponsor's representative must be acceptable to PPD and be approved (along with the protocol, and any other necessary documentation) by the Institutional Review Board/Independent Ethics Committee and other regulatory bodies as applicable.

## **5.2. Subject identification and randomization**

### **5.2.1. Subject identification**

Subject identification numbers will be assigned sequentially to the subjects who have consented or provided assent with consent from each subject's parent(s)/LAR(s) to participate in the study, according to the range of subject identification numbers allocated to each study center.

### **5.2.2. Randomization of treatment**

#### **5.2.2.1. Treatment allocation to the subject**

The treatment numbers will be allocated by dose.

##### **5.2.2.1.1. Study group and treatment number allocation**

The target will be to enroll approximately 500 eligible subjects who will be randomly assigned to 5 study groups in a (1:1:1:1:1) ratio (approximately 100 subjects in each study group).

The enrollment will be performed to ensure equal distribution of the population across the 2 age strata of 10 to 17 years and 18 to 25 years in each study group (i.e., of the approximately 100 subjects in each study group, approximately 50 subjects will be aged 10 to 17 years and approximately 50 subjects will be aged 18 to 25 years).

The randomization list will be generated using MATEX, a program developed by GSK for use in SAS. Central randomization will be performed using SBIR.

Allocation of the subject to a study group at the investigator site will be performed using the SBIR system. Within each age stratum (10 to 17 years and 18 to 25 years), the randomization algorithm will use a minimization procedure accounting for center. Minimization factors will have equal weight in the minimization algorithm.

After obtaining the signed and dated ICF/IAF from the subject/subject's parent(s)/LAR(s) and having checked the eligibility of the subject, the study staff in charge of the vaccine(s) administration will access SBIR. Upon providing the age (10 to 17 years and 18 to 25 years) and the subject identification number, the randomization system will determine the study group and will provide the treatment number to be used for each dose.

The number of each administered treatment must be recorded in the eCRF on the Vaccine Administration form/screen.

When SBIR is not available, please refer to the SBIR user guide or the Study Procedures Manual (SPM) for specific instructions.

After the target of 50 subjects per age group stratification (10 to 17 years or 18 to 25 years) has been reached in any of the 5 study groups, the enrollment will be frozen for that age and study group.

#### **5.2.2.1.2. *Treatment number allocation for subsequent doses***

For each dose subsequent to the first dose, the study staff in charge of the vaccine(s) administration will access SBIR, provide the subject identification number, and the system will provide a treatment number consistent with the allocated study group.

The number of each administered treatment must be recorded in the eCRF on the Vaccine Administration form/screen.

### **5.3. Method of blinding**

This will be an open-label study.

The laboratory in charge of the laboratory testing will be blinded to the treatment, subject, and visit number, and codes will be used to link the subject, visit, and study (without any link to the treatment attributed to the subject) to each sample.

### **5.4. General study aspects**

Supplementary study conduct information not mandated to be present in this protocol is provided in the accompanying SPM. The SPM provides the investigator and the site personnel with administrative and detailed technical information that does not impact the safety of the subjects.

### **5.5. Outline of study procedures**

Refer to the list of study procedures in [Table 4](#).

**Table 4 List of study procedures**

Epoch	Epoch 001					
Type of contact	Visit 1	Safety call 1	Visit 2	Visit 3	Safety call 2	Visit 4
Time points	Day 1	Day 15	Day 31	Day 61	Day 75	Day 91
Sampling time points	Pre-Vacc 1		Post-Vacc 1			Post-Vacc 2
Informed consent	● 					
Check inclusion/exclusion criteria	● 			○		
Collect demographic data	● 					
Medical history	● 					
History directed physical examination	○					
Physical examination	○			○		
Urine pregnancy test	● 			● 		
Check contraindications and warnings and precautions to vaccination	●			● 		
Pre-vaccination body temperature	●			● 		
Measure/record height and weight	● 					
Study group and treatment number allocation	●					
Recording of administered treatment number	●			● 		
Blood sampling (~20 mL)	● 		●			● 
Vaccine(s) administration	●			● 		
Record any concomitant medications/vaccinations	●	●	●	● 	● 	● 
Record any intercurrent medical conditions	●	●	●	● 	● 	● 
Distribution of pDiary	○			○ 4,6		
Review of pDiary			○	○ 4		○ 4
Return of pDiary			○ 6	○ 4,6		○ 4,6
Recording of AEs within 30 minutes post-vaccination	●			● 		
Recording of solicited AEs (days 1 to 7 post-vaccination)	●			● 		
Recording of unsolicited AEs (days 1 to 30 post-vaccination)	●	●	●	● 	● 	● 
Recording of AEs, SAEs, medically attended AEs, AESI, and AEs leading to withdrawal	● 	●	●	●	●	●
Recording of AEs/SAEs related to study participation or to a concurrent GSK medication/vaccine	● 	●	●	●	●	●
Recording of SAEs related to study vaccine(s)	● 	●	●	●	●	●
Study conclusion						●

Activities that can be performed at a separate visit before Visit 1 (maximum 5 days before the Visit 1). All AEs/SAEs, including those related to study participation or to a concurrent GSK medication/vaccine should be recorded starting from informed consent signature. Inclusion/exclusion criteria should be re-checked prior to vaccination at Visit 1.

For women of childbearing age. The pregnancy test is to be performed locally onsite.

A pregnancy test is mandatory even if performed during a prior separate visit.

This study procedure will not be performed at this time point for the MenACWY group, administered only 1 dose of vaccine at Visit 1 (no Visit 3 performed)

Blood sample collection will be performed before vaccine(s) administration.

Subjects who receive a single dose of MenACWY only will return their pDiary at Visit 2 (Day 31). All subjects in the other treatment groups will return their first pDiary at Visit 3 (Day 61) and will receive a second pDiary for the remainder of the study.

● is used to indicate a study procedure that requires documentation in the individual eCRF.

○ is used to indicate a study procedure that does not require documentation in the individual eCRF.

AE = adverse event; AESI = adverse event of special interest; eCRF = electronic case report form; GSK = GlaxoSmithKline; Pre-Vacc: pre-vaccination; Post-Vacc: post-vaccination; SAE = serious adverse event

Whenever possible, the investigator should arrange study visits within the interval described in [Table 5](#).

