#### **5.6.13.1. Subject diary**

A pDiary hereafter referred to as Subject Diary will be used in this study to capture solicited AEs. The subject should be trained on how and when to complete each field of the Subject Diary.

Subject Diary training should be directed at the individual(s) who will perform the measurements of AEs and who will enter the information into the Subject Diary. This individual may not be the subject/subject's parent(s)/LAR(s), but if a person other than the subject/subject's parent(s)/LAR(s) enters information into the Subject Diary, this person's identity must be documented in the Subject Diary. Any individual that makes entries into the Subject Diary must receive training on completion of the Subject Diary at the time of the visit when Subject Diary is dispensed. This training must be documented in the subject's source record.

The same individual should complete the Subject Diary throughout the course of the study.

The subject/subject's parent(s)/LAR(s) should be trained on how to self-measure local solicited AEs and body temperature.

The measurement of solicited local AEs is to be performed using the ruler provided by the site.

The subject/subject's parent(s)/LAR(s) should be instructed how to perform body temperature (preferably axilla) measurement using the thermometer provided by the site, and to record the body temperature in the evening. If the subject feels unusually hot or cold during the day, the subject or parent(s)/LAR(s) should check the body temperature. If the subject has a fever, the highest body temperature observed that day should be recorded in the Subject Diary.

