### 11.2. Subject diary

Subject Diaries will be the only source document allowed for solicited local and systemic AEs (including body temperature measurements), starting after the initial 30-minute post-vaccination period at the clinic. The following additional rules apply to documentation of safety information collected in the Subject Diary.

The investigator or delegated staff should monitor the Subject's Diary status throughout the study for compliance and any solicited local and systemic AEs that were of concern to the subject.

- No corrections or additions to the information recorded by the subject/parent(s)/LAR(s) within the Subject Diary will be allowed after it is delivered to the site.
- Any blank or illegible fields on the Subject Diary must be described as missing in the eCRF.

The following additional rules apply to documentation of Subject Diary information collected in the eCRFs:

The site must enter all readable entries in the Subject Diary into the eCRF, including those values that may be biologically implausible (e.g. body temperature: 400°C).

Any illegible or implausible data should be reviewed with the subject/parent(s)/LAR(s). If an underlying solicited or unsolicited AE is described on review with the subject, this should be described in the source document and reported as an unsolicited AE in the Adverse Event eCRF (e.g. if the subject above confirms body temperature of 40°C on the day in which body temperature: 400°C was written into his/her Subject Diary, this fever of 40°C should be recorded in the Adverse Event eCRF).

Any newly described safety information (including a solicited AE) must not be written into the Subject Diary and must be described in the study file as a verbally reported AE. Any AE reported in this fashion must be described as an unsolicited AE and therefore entered on the Adverse Event eCRF.

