This study procedure will not be performed at this time point for the MenACWY group, administered only 1 dose of vaccine at Visit 1 (no Visit 3 performed)

Blood sample collection will be performed before vaccine(s) administration.

Subjects who receive a single dose of MenACWY only will return their pDiary at Visit 2 (Day 31). All subjects in the other treatment groups will return their first pDiary at Visit 3 (Day 61) and will receive a second pDiary for the remainder of the study. (Amended 15 May 2018)

● is used to indicate a study procedure that requires documentation in the individual eCRF.

○ is used to indicate a study procedure that does not require documentation in the individual eCRF.

AE = adverse event; AESI = adverse event of special interest; eCRF = electronic case report form; GSK = GlaxoSmithKline; Pre-Vacc: pre-vaccination; Post-Vacc: post-vaccination; SAE = serious adverse event

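### Two-dose subjects keep the completed dose-1 diary until Visit 3 although it is reviewed at Visit 2, so the solicited data of those who do not return after Visit 2 can be lost

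*Protocol*

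**What the plan says.** The single-dose group and the four two-dose groups (MenABCWY, rMenBOMV+ACWY_S, rMenBOMV+ACWY_D, rMenBOMV) have different rules for handing in the diary. Footnote 6 to protocol Table 4, which also stands under Synopsis Table 5, says "Subjects who receive a single dose of MenACWY only will return their pDiary at Visit 2 (Day 31" and then "All subjects in the other treatment groups will return their first pDiary at Visit 3 (Day 61) and will receive a second pDiary". SAP Table 10 has the same rule: "All subjects in the other treatment groups will return their first pDiary at Visit 3 (Day 61".

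Protocol Section 5.6.13.1 says the diary "will be used in this study to capture solicited AEs", and Section 8.1.3 sets the period at 7 consecutive days. In Table 4 the row "Review of pDiary" has an open circle at Visit 2 for every group. That symbol "is used to indicate a study procedure that does not require documentation in the individual eCRF".

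Protocol Section 11.2 makes the diary the exclusive source: "Subject Diaries will be the only source document allowed for solicited local and systemic AEs (including body temperature measurements". The rest of that sentence starts the rule after the 30 minutes of observation in the clinic.

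**The concern.** The dose-1 diary is finished about three weeks before Visit 2 and is due for review there, yet the schedule leaves it with the subject for about another month. Nothing in the protocol or SAP requires it to be collected, copied or transcribed at Visit 2, or retrieved from a subject who misses Visit 3. For non-returners, protocol Section 9.2.1 provides three telephone calls and a certified letter, without mentioning the diary.

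The loss may be related to the outcome. The protocol lists a solicited AE as a reason for leaving the study (Section 9.2.1) and for stopping vaccination (Section 9.2.2), so it foresees that reactions can keep people away. That such subjects would also fail to bring back the diary is an inference, but a reasonable one. The exposure is also uneven: MenACWY diaries come in at Visit 2, those of the other four groups at Visit 3. At stake is the completeness of the dose-1 solicited tables in the four two-dose groups.

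**Working it through.** The plan gives no figure for diary loss or dropout, so there is nothing of its own to reproduce. The check sets the passages side by side and then sizes the loss under stated assumptions.

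**1. Timing (protocol Table 5).** Diary complete: day 7. Visit 2: 23 to 40 days after Visit 1. Visit 3: 53 to 70 days after Visit 1. On the nominal schedule the gap between review and return is 61 − 31 = 30 days.

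**2. What is recorded elsewhere.**
- Reactions in the first 30 minutes go on the eCRF (SAP 9.1.1).
- Solicited AEs that last beyond day 7, are medically attended, lead to withdrawal or are serious also go on the Adverse Event eCRF (protocol 8.1.3.3).
- Reactions reported verbally go there as unsolicited AEs (protocol 11.2).

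What remains with the diary alone is every other reaction that starts after 30 minutes. The Adverse Event entries do not supply the daily graded data behind the solicited tables.

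**3. Who is exposed.** Stopping vaccine is not the same as leaving the study (protocol 9.2.2), and Table 4 also marks diary return at Visit 4. The exposed subjects are those who attend Visit 2 and never come back to the site.

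**4. Denominator.**
- Any solicited AE data place a subject in the Solicited Safety Set (SAP 4.4.3), so a 30-minute record can be enough.
- By default, SAP percentages use all subjects of the group in the analysis set (SAP 4).
- SAP 4.3 removes subjects with missing data from the denominator only in its missing-at-random branch, which needs at least 20% missing and a Fisher p-value below 0.05. Below 20% nothing changes.
- Protocol 10.6 instead counts only subjects or doses with documented data.

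**5. Size.** Inputs: 4 groups × 100 = 400 two-dose subjects (protocol 4.1). Assumptions: a share d of 1% to 10% is lost after Visit 2, and the true rate p of some common reaction is 80%.
- Diaries at risk = 400 × d.
- Reported rate with the SAP default, if lost subjects count as having no event and loss is unrelated to reactions = p × (1 − d).
- Reported rate on documented subjects, per group of 100 = (80 − r) / (100 − 100d), where r is the number of lost subjects who had the reaction.

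| d | Diaries of 400 | Per group | SAP default | Documented only, loss unrelated | Documented only, all lost subjects had the reaction |
|---|---|---|---|---|---|
| 1% | 4 | 1 | 79.2% | 80.0% | 79/99 = 79.8% |
| 2% | 8 | 2 | 78.4% | 80.0% | 78/98 = 79.6% |
| 5% | 20 | 5 | 76.0% | 80.0% | 75/95 = 78.9% |
| 10% | 40 | 10 | 72.0% | 80.0% | 70/90 = 77.8% |

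A loss of 19 per group of 100 would still lie below the 20% trigger, and 80% would then read 0.80 × 0.81 = 64.8%. The documented-only denominator removes the bias when loss is unrelated to reactions, but not when it is related.

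**The case against.** The strongest reply is that a badly tolerated first dose does not simply vanish. A solicited AE that leads to withdrawal must be entered as an AE, the withdrawal reason is coded, and such subjects are followed until resolution (protocol 8.1.3.3 and 9.2.1). The Day 15 safety call asks about unsolicited and medically attended events. SAP 4.3 tabulates subjects without data per interval with a Fisher p-value, so unequal loss would be seen. All four two-dose groups share one schedule, so comparisons among them are symmetric in this respect. Amendment 1 deliberately clarified diary distribution and return, and the Study Procedures Manual, which is not available here, may tell sites to copy the diary. All of this stands and limits the point. It does not restore the daily graded data, and seeing the loss is not correcting it.

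Three stronger readings are tempting, and the documents do not support them.

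- A reader might infer that everyone who misses dose 2 takes away every trace of the dose-1 reactions. Steps 2 and 3 of the working show otherwise: several kinds of reaction are recorded elsewhere, and an unvaccinated subject can still hand in the diary at Visit 3 or Visit 4.
- A reader might infer that two-dose subjects can fill blanks from memory between Visit 2 and Visit 3, because Section 11.2 says that no change to entries "within the Subject Diary will be allowed after it is delivered to the site". But the same section keeps newly described safety information out of the diary and has blank fields entered as missing. Whether bringing the diary to the Visit 2 review counts as delivery is not stated.
- A reader might infer that the longer holding time makes dose-1 data less comparable with dose-2 data. Both doses have the same 7-day recording period and the same reminder calls. How long a finished diary stays at home does not change how it was filled in.

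**Conclusion.** The gap is real but limited. For two-dose subjects who do not come back after Visit 2, the schedule gives up a completed diary that the site was due to review, and with it the sole permitted source for non-escalated dose-1 reactions that start after 30 minutes.

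The number of diaries at risk, about 4 to 40 of 400, rests wholly on an assumed 1% to 10% loss after Visit 2 and on those subjects having brought the diary to that visit. The shift in a reported rate depends further on the denominator used and on how many of the lost subjects had the reaction. The documents give neither a dropout rate nor any severity pattern among non-returners, so a specific bias in severe-reaction rates cannot be calculated from them. Nor can it be claimed that the rates will be biased low under the protocol's own denominator: if loss is unrelated to reactions, they are not.

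The hSBA analyses are untouched. Only the secondary safety objective is affected, and its analysis is descriptive. The change is worth making because it costs very little, not because the expected bias is known to be large.

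**What to change.** Change footnote 6 and the diary-return row in Synopsis Table 5, protocol Table 4 and SAP Table 10 so that subjects in all five groups return the first diary at the review already scheduled for Visit 2. The second diary is still issued at Visit 3 and returned at Visit 4. If there is a reason to leave the first diary with the subject, require the site to copy it at Visit 2 instead.

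Reconcile SAP Sections 4 and 4.3 with protocol Section 10.6, stating which denominator applies to solicited events when fewer than 20% of subjects lack data.

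Cost: one footnote, one table row in three tables, and one clarifying sentence on the denominator. No visit or staff are added. The downside is that two-dose subjects hold no diary between Visit 2 and Visit 3. This matters little, since protocol Sections 5.6.13.1 and 8.1.3 assign the diary only to the solicited events of the 7 days after vaccination, and copying at Visit 2 avoids it altogether.
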